Prostate artery embolization (PAE) was originally developed to treat hemorrhage after prostate biopsy or surgery. The procedure is modeled after uterine artery embolization (UAE) for the treatment of fibroids in women. Fibroid embolization is commonly performed at our institution and has been proven safe when compared to surgical management with a shorter hospital stay and quicker return to routine activity (3). In 2000, DeMeritt *et al* performed PAE to treat a patient with acute urinary retention and hematuria. After treatment, voiding improved and the prostate decreased in size 40% in 1 year (4). Animal studies show prostate size reduction after embolization with no major procedure related complications (5,6).

In the last 5 years, several studies from outside the United States demonstrated excellent technical and clinical success of PAE treating moderate to severe lower urinary tract symptoms (LUTS) due to BPH. These studies showed reduced prostate size and improved clinical symptoms scores after embolization with minimal side-effects. This resulted in Embosphere microspheres (Merit Medical; South Jordan, UT) receiving CE marking in Europe for PAE. The Society of Interventional Radiology (SIR) considers prostate artery embolization an emerging research priority and supports the performance of high-quality clinical research (7). The FDA recognizes this promising area of research and has published study guidelines for new device application with descriptions of patient selection and safety reporting (8).

The first study of PAE to treat BPH in humans was performed in 2010. Prostate volume reduction and clinical improvement was demonstrated in 2 patients with acute urinary retention (9). Pisco *et al* initially treated 15 patients with moderate to severe BPH and showed prostate volumes decreased 22% in 1 month with clinical severity score improved 6.7 points (10). They later published their expanded series of 255 patients with clinical success of 81.9% at 1 month, 75.2% at 1 year, and 72% at 2 and 3 years (11). Medium and long-term results were recently published in 630 patients with 81.9% and 76.3% cumulative success (12). The only major complication was a small area of bladder wall ischemia that required resection. Carnevale *et al* published the results of 11 patients treated with acute urinary retention treated with PAE. Clinical success was 91% with prostate volume decreased 30% after 1 year (13). There were no major complications or adverse events.

The first United States trial published in 2013 and updated in 2014 reports the treatment of 20 patients with symptomatic BPH. 90% technical success and 95% clinical success was reported at 1 month with prostate volume decreased 18% at 3 months (14). There were no major complications. Minor complications include a mild self-limited post-embolization syndrome consisting of pain, nausea, and malaise. Self-limited hematuria, dysuria, urinary frequency, and pelvic pain have also been reported. Gao *et al* published a prospective randomized trial comparing PAE to TURP in 114 patients (15). Both procedures demonstrated significant clinical improvement. The PAE group had more clinical failures (9.4% vs 3.9%) but reduced procedural bleeding, less need for urethral catheterization, and shorter hospital stay.

Prostate artery embolization has been performed with nonspherical PVA particles (10,11,12,15), tris-acryl gelatin microspheres (9,13), and hydrogel microspheres with a proprietary coating (14). No studies have been performed to directly compare the efficacy of these embolic agents. At UC San Diego we frequently

use microspheres for procedures requiring arterial embolization. We are experienced with a wide range of embolic materials. We propose using 300-500 μm and 100-300 μm Embospheres (Merit Medical; South Jordan, UT) as the embolic agent in this study.

PAE for LUTS attributed to BPH provides a minimally invasive treatment option with several advantages compared to surgical therapy. Excellent technical and clinical success is reported. The procedure is minimally invasive and can be performed as an outpatient procedure with minimal pain. Side effects are mild and self-limited, and major complications are rare. PAE is a technically challenging procedure. The clinical success rate is reduced when only unilateral embolization is possible, and poor technique could result in nontarget embolization resulting in pain or pelvic organ dysfunction. Further investigation is necessary to determine the safety of this procedure, the appropriate indications, the ideal embolic material, the durability of effect, and to directly compare this technique with surgical management.

2. Study Objectives

2.1 Primary Objective

The primary objective of this investigation is to evaluate improvement of benign prostatic hyperplasia (BPH) symptoms as assessed by the International Prostate Symptom Score (IPSS) after prostate artery embolization (PAE) with Embosphere® Microspheres in 20 patients with 24 months follow-up.

2.2 Secondary Objectives

The secondary objectives of this investigation are to assess the following outcomes, compared to baseline values when appropriate:

1. PAE-related adverse events
2. Overall adverse events
3. Prostate volume as determined by transrectal ultrasound
4. Serum prostate specific antigen (PSA) level
5. Post void residual volume (PVR) as determined by transabdominal ultrasound
6. Post void residual urinary volume (PVR) as determined by uroflowmetry
7. Peak urine flow rate (Qmax) as determined by uroflowmetry
8. Sexual function as determined by the International Index of Erectile Function (IIEF)

3. Patient Population

3.1 Inclusion Criteria

Patients must meet all of the following inclusion criteria in order to be eligible for this study.

1. Provided informed consent
2. Age greater than 50 years and less than 85 years
3. Prostate volume between 40 and 300 cm³
4. Diagnosis of BPH with moderate to severe lower urinary tract symptoms (LUTS) defined as at least one of the following:
 - a. IPSS greater than 18
 - b. IPSS Quality of Life (QoL) assessment greater than 3
 - c. Qmax less than 12 mL/sec
5. Refractory or intolerant to medical management
6. Ineligibility for or refusal of surgical management
7. One of the following criteria:
 - a. Baseline prostate specific antigen (PSA) ≤ 2.5 ng/mL
 - b. Baseline PSA > 2.5 ng/mL and ≤ 10 ng/mL AND free PSA $\geq 25\%$ of total PSA
 - c. Baseline PSA > 2.5 ng/mL and ≤ 10 ng/mL AND free PSA $< 25\%$ of total PSA AND negative 12 core prostate biopsy in the past 12 months
 - d. Baseline PSA > 10 ng/mL AND negative 12 core biopsy within the past 12 months

3.2 Exclusion Criteria

Patients that meet any of the following exclusion criteria will not be eligible for this study.

1. History of prostate, bladder or rectal malignancy. Biopsy proven urethral cancer.
2. History of rectal disease
3. Neurogenic bladder disorder due to multiple sclerosis, Parkinson's disease, spinal cord injury, diabetes, etc., as demonstrated on urodynamic testing.
4. Detrusor muscle failure, urethral stenosis, or urinary obstruction due to causes other than BPH, as demonstrated on urodynamic testing
5. Bladder diverticula greater than 5 cm or bladder stones greater than 2 cm
6. Cystolithiasis within the past three months
7. Baseline serum creatinine greater than 1.8
8. Evidence of tortuous or atherosclerotic blood vessels
9. Presence of collateral vessel pathways potentially endangering normal territories during embolization that cannot be bypassed with the microcatheter
10. Active urinary tract infection, interstitial cystitis, or prostatitis within the last 5 years
11. Coagulation disturbances not normalized by medical treatment
12. Allergy to iodinated contrast agents not responsive to steroid premedication regimen
13. Previous radical pelvic or rectal surgery, or pelvic irradiation
14. Prior surgical prostate intervention
15. Treatment with beta-blocker, antihistamine, anticonvulsant, or antispasmodic medication within 1 week of treatment UNLESS there has been a stable voiding pattern while medicated with the drug(s) for 6 months
16. Use of prostate active medications, including alpha blockers, anti-cholinergics, androgens, anti-androgens, gonadotropins-releasing hormonal analogs, PDE5-inhibitors, 5-alpha reductase inhibitors within 2 months of intervention, unless the medication is necessary to avoid symptom exacerbation and disability, in this case medication should not be initiated or dose adjusted within 1 month of study enrollment and dose should not be adjusted during the study period
17. Interest in future fertility
18. Mental condition or disorder that interferes with participants' ability to provide written informed consent

19. Current severe or uncontrolled disease (metabolic, hematologic, renal, hepatic, pulmonary, neurologic, cardiac, infectious or gastrointestinal) that in the Investigator's judgment makes the patient unsuitable for trial inclusion due to increased risk of complications
20. Known immunosuppression
21. Life expectancy less than 6 months

4. Study Design

This is a phase I/II, single center, prospective, single arm, investigational study to evaluate the safety and efficacy of prostate artery embolization (PAE) for treatment of severe lower urinary tract symptoms (LUTS) related to benign prostatic hyperplasia (BPH) in patients with prostate size between 40 and 300 cm³ that have either failed or are intolerant to medical management. Patients will be considered enrolled in the study once they have provided informed consent. A total of 20 patients will be enrolled in the single treatment arm of the study. Treated participants will be followed for no less than 24 months.

The study will involve a screening period in which patient eligibility is determined. Once eligibility is confirmed, patients will undergo PAE with Embosphere Microspheres within 4 weeks of baseline prostate ultrasound. Following treatment, patients will return for follow-up visits at 1, 6, 12, and 24 months post PAE. At each of these visits, patients will complete the International Prostate Symptom Score (IPSS) and International Index of Erectile Function (IIEF) questionnaires, undergo a physical exam, transrectal prostate ultrasound, transabdominal prostate ultrasound, uroflowmetry and laboratory evaluations, and medication and adverse event reviews.

The primary objective of the study will be improvement of BPH symptoms as assessed by the IPSS questionnaire. Patients will continue to be followed according to the institutional standard of care follow-up schedule after they complete the study.

Safety will be evaluated throughout the study by assessing adverse events and findings on physical examination. Concomitant medication usage will also be assessed.

5. Treatments and Assessments

Study participants will be treated with a single PAE procedure performed with Embosphere Microspheres. The microspheres will be mixed with a contrast agent and will be delivered to the arteries supplying the prostate via a microcatheter. The occlusion endpoint will be stasis as defined as persistent contrast in the feeding vessel that persists for 5 heartbeats. A complete description of the technical protocol to be followed is provided in Appendix C.

After treatment with PAE, follow-up visits will take place at 1, 6 12, and 24 months, ± 2 weeks, from the day of treatment. A Schedule of Events and Study Flow Chart are provided in Appendices A and B, respectively. Cystoscopy and/or anoscopy will be performed for signs or symptoms of bowel or bladder injury, including hematuria, blood per rectum, or greater than expected pelvic pain at any time during the study protocol. Certain medical conditions, such as neurogenic bladder, detrusor failure, and urethral stenosis, may mimic LUTS due to BPH. Urodynamic testing will be obtained at baseline for patients with clinical symptoms or history concerning for these conditions.

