If a patient is withdrawn or discontinued from the study, the reason for withdrawal will be recording in the source documents and on the End of Study CRF. All patients withdrawn from the study will be encouraged to complete, if possible, all clinical evaluations scheduled for the 12 month follow-up visit. All adverse events will be followed as described in Section 7. Patients who are withdrawn from the study for any reason will not be replaced. The Principle Investigator may terminate the study at any time.

7. Adverse Events

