9.5.1 International Prostate Symptom Score (IPSS)

The primary efficacy outcome will be based on the IPSS. The IPSS is a frequent used, validated, 8 item (7 symptom burden questions and 1 quality of life question) instrument which can be serially performed to compare the progression of symptoms and their severity over months and years. Patients are asked to assess how often they have experienced the following 7 symptoms in the past month: incomplete emptying, frequency, intermittency, urgency, weak urine stream, straining and nocturia. The response categories range from 0=Not at all to 5=Almost always. The total IPSS score is calculated by summing the responses for the 7 symptom burden items. The eighth item is an assessment of patient quality of life due to LUTS and does not contribute to the IPSS score calculation.

Patients will be classified into one of 3 symptom severity categories based on their total IPSS score as follows:

- Mildly symptomatic: 0-7
- Moderately symptomatic: 8-19
- Severely symptomatic: 20-35

The IPSS total score will be summarized for the baseline, 1 month, 6 month and 12 month time points, including change from baseline. Change from baseline will be calculated as post baseline IPSS score minus baseline IPSS score. A negative value indicates symptom improvement. 95% confidence intervals will be calculated for the mean change from baseline to the post baseline time points. For informational purposes, IPSS scores will also be summarized separately for patients that receive unilateral and bilateral PAE if there are sufficient numbers in both groups.

The primary efficacy analysis will be the change in IPSS total score from baseline to 12 months post PAE for the ITT population. A Paired-Sample Wilcoxon Signed Rank Test will be used to assess the statistical significance of the change from baseline to 12 months post PAE. A secondary analysis of the proportion of patients who have improved by at least one IPSS symptom category (i.e., severe to moderate, severe to mild, or moderate to mild) from baseline to 12 months post PAE will also be performed. A 95% confidence interval will be calculated for the proportion. The proportion of patients improving at least 3 points on the IPSS total score at the 12 month time point will also be summarized and the corresponding 95% confidence interval will be calculated.

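### The life-expectancy exclusion (under 6 months) is shorter than the 12-month primary endpoint, and no other criterion closes the gap; a minor point with a one-number fix

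*Combined protocol and SAP*

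**What the plan says.** Section 3.2, item 21, excludes men with "Life expectancy less than 6 months". This is the only eligibility criterion that refers to survival.

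The horizons of the study are longer:

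- Section 9.5.1: "The primary efficacy analysis will be the change in IPSS total score from baseline to 12 months post PAE for the ITT population".
- Sections 7.1 to 7.3: adverse events are recorded, and serious events including death from any cause are reported, over 12 months after the procedure.
- Section 2.1 states the primary objective "in 20 patients with 24 months follow-up", and Section 4 says "Treated participants will be followed for no less than 24 months". Under Sections 9.1 and 9.7, however, the 24-month data are analysed apart from the 12-month results, and summarising them is optional.

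On men who do not reach month 12, Section 6 lists death among the reasons for withdrawal and adds that "Patients who are withdrawn from the study for any reason will not be replaced". Section 9.5.7 fills a missing IPSS in the ITT analysis by last observation carried forward, using baseline when there is no valid later value. Section 9.3.2 requires valid 12-month IPSS for the Evaluable Population.

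**The concern.** An eligibility rule on life expectancy normally serves to make the primary outcome observable. Here the rule stops at half the time to that outcome, and the protocol gives no reason for choosing 6 months.

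The trial is small, has a single arm and replaces nobody. A death before month 12 therefore turns an intended 12-month measurement into a month-1, month-6 or baseline value. The fallback in Section 5.3 (questionnaires by telephone, email or mail) can rescue the IPSS of a man who does not attend, but not of a man who has died. With no control arm, a death from an illness already known at entry also appears in the safety table with nothing to compare it with.

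**Working it through.** The plan states no figure to reproduce: Section 9.2 says that no formal sample size calculation was done, and there is no assumption about mortality or dropout. The check has three parts.

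**1. Threshold against horizon.**

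- Primary endpoint: 12 − 6 = 6 months short.
- Planned follow-up: 24 − 6 = 18 months short.

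**2. Does another criterion close the gap?**

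- Item 19 of Section 3.2 covers severe or uncontrolled disease, but only where in the investigator's judgment it "makes the patient unsuitable for trial inclusion due to increased risk of complications". The ground is complication risk, not survival, and its list of disease types does not name cancer.
- Item 1 covers cancer only at certain sites: "History of prostate, bladder or rectal malignancy. Biopsy proven urethral cancer".
- Section 3.1 sets age as "Age greater than 50 years and less than 85 years" and admits men who are ineligible for surgery as well as men who refuse it. Neither is a survival requirement.

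So a man expected to live 6 to 12 months is not excluded on that ground, though he may be excluded on another.

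**3. Size of the effect, taking 20 treated men.**

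- *Share of the sample.* 1/20 = 5%. One death is 5% in the death line of Section 9.6.1, and one misclassified man moves either responder proportion in Section 9.5.1 by 5 percentage points.
- *Mean IPSS change.* If the carried score differs from the unobserved 12-month score by d points, the mean change moves by d/20. The documents give no value for d. With an assumed 5 to 10 points: 5/20 = 0.25 and 10/20 = 0.5. Section 9.5.1 counts an improvement of at least 3 points as a response, so the shift is at most 0.5/3, about 17% of that.
- *Wilcoxon test.* The signed-rank test uses signs and ranks. Unless the carried score reverses the sign of that man's change, only his rank and those near it move, so the result changes little.
- *Evaluable trigger.* Section 9.5 adds an Evaluable analysis when more than 15% of men are excluded. 3/20 is exactly 15% and does not exceed it; 4/20 = 20% does. Four exclusions are needed, and one man is a quarter of that count.
- *Chance that deaths alone reach the trigger.* The binomial probability of 4 or more deaths among 20 before month 12, for assumed per-man risks:

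| Assumed risk of death before month 12 | P(4 or more of 20) |
|---|---|
| 2% | 0.06% |
| 5% | 1.6% |
| 10% | 13% |
| 20% | 59% |

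- *Who would be lost.* As an illustration, assume exponential survival, S(t) = 0.5^(t/median). A median of 6 months gives S(12) = 0.5^2 = 25%. A median of 9 months gives 0.5^(12/9) = 40%. A median of 12 months gives 50%. A man near the present threshold would more often than not lack a 12-month score.

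**The case against.** **Few such men will enrol.** PAE for BPH is elective, and Section 3.2 already removes men with raised creatinine, diseased vessels, uncorrected coagulation problems, immunosuppression, or serious organ disease judged to raise complication risk. Many men with less than a year to live would meet one of these. This stands as partial mitigation and is the main reason the point is minor. It does not supply a survival requirement, and some cancers are not covered.

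**The analysis already copes.** Section 9.5.7 plans multiple imputation as a sensitivity analysis. Section 7.2 grades attribution in five classes, and Section 9.6.1 tabulates related events separately, so an unrelated death would not appear as a related serious event. This also stands in part. But imputation is conditional on the data being judged missing at random, and the primary analysis remains the carried-forward one.

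Three stronger readings are tempting, and the documents do not support them.

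- *That the threshold must be 24 months.* A man who dies between months 12 and 24 can supply his 12-month IPSS, need not leave the Evaluable Population, and dies outside the 12-month safety window. Only the separately handled long-term data are affected.
- *That carrying forward must flatter PAE.* Section 1 cites a series in which clinical success fell from 81.9% at 1 month to 75.2% at 1 year, which makes this possible. But that is a success rate in a cohort, not the IPSS course of a dying man, and a man with no post-baseline value is entered as unchanged.
- *That any death would stop the trial.* Section 7.2 names procedure-related death, not death from any cause. Nor is crossing the 15% trigger a harm: it only adds a secondary analysis.

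**Conclusion.** The mismatch is real and follows from the text alone: the life-expectancy criterion falls 6 months short of the primary endpoint and of the safety window, and nothing else in Section 3 requires expected survival that far.

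The consequence is minor. Each man who dies before month 12 costs one observed primary outcome in 20, moves the mean change by an estimated 0.25 to 0.5 points, and adds 5% to the death line. The shift rests on an assumed difference of 5 to 10 points; the percentages rest on 20 treated men. How many men would be affected cannot be derived from the documents, and the survival and mortality figures above are illustrations. Nothing here suggests that the primary test would be overturned.

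**What to change.** Reconcile exclusion 21 with the primary endpoint by raising the life-expectancy threshold to at least 12 months. Count it from the planned date of PAE, since screening may come up to 4 weeks earlier. If the sponsor has a reason for 6 months, state it in Section 3.2.

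A 24-month threshold is optional. It would match the follow-up in Sections 2.1 and 4, but it would protect only the separately summarised long-term data.

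The cost is one number in the criteria, and a few men become ineligible. No change to the analysis is needed.

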5.1 Visit -1: Screening/Baseline (within 4 weeks of PAE)

Patients meeting all of the inclusion and none of the exclusion criteria listed in Section 3 are eligible for participation in this study.

Prior to enrollment, each patient will have the following assessments performed:

- Obtain written informed consent
- Medical history, including demographics
- Physical exam including vital signs
- Recording of concurrent medical conditions
- IPSS and IIEF questionnaires
- Transrectal ultrasound (TRUS) of the prostate
- Transabdominal ultrasound (TAUS) of the bladder
- Uroflowmetry to assess Qmax
- Laboratory evaluations, including a complete blood count (CBC), complete metabolic panel (CMP), urinalysis, urine culture, and prostate specific antigen (PSA)
- Preprocedural CT angiography of the pelvis
- Prostate biopsy, if indicated by protocol
- Recording of concomitant medications
- Anoscopy if clinically indicated for evaluation of suspected rectal disease

5.2 Visit 1: Prostate Artery Embolization (PAE)

The PAE procedure will be performed within 4 weeks of baseline prostate ultrasound. PAE with Embosphere Microspheres will be performed according to the technical procedure provided in Appendix C.

Treatment data recorded will include the following:

- Total fluoroscopy time
- Total radiation dose
- Number and origins of arterial supply
- Volume and size of embolic material delivered
- Evidence of collateral blood supply
- Duration of hospitalization
- Sedative medications administered
- Patient pain score before and after procedure

- Procedure adverse events

5.3 Visits 2, 3, 4: 1 Month, 6 Months, 12 Months (4 weeks, 24, 52 ± 2 weeks post PAE)

Patients will have the following assessments performed:

- Physical exam, including vital signs
- IPSS and IIEF questionnaires
- TRUS of the prostate
- TAUS of the bladder
- Laboratory evaluations, including a complete blood count (CBC), complete metabolic panel (CMP), urinalysis, urine culture, and prostate specific antigen (PSA)
- Uroflowmetry to assess Qmax
- Cystoscopy, if clinically indicated
- Proctoscopy, if clinically indicated
- Review of concomitant medications and adverse events

Patients who are unable or unwilling to return for follow-up will be contacted by telephone, email, or mail to administer the IPSS and IIEF questionnaires, and to report any new treatments for BPH and/or LUTS.

5.4 Visit 5 (Long Term Follow-Up): 24 Months (104 ± 2 weeks post PAE)

Patients will have the following assessments performed:

- Physical exam, including vital signs
- IPSS and IIEF questionnaires
- TRUS of the prostate
- TAUS of the bladder
- Laboratory evaluations, including a complete blood count (CBC), complete metabolic panel (CMP), urinalysis, urine culture, and prostate specific antigen (PSA)
- Uroflowmetry to assess Qmax

Patients who are unable or unwilling to return for follow-up will be contacted by telephone, email, or mail to administer the IPSS and IIEF questionnaires, and to report any new treatments for BPH and/or LUTS.

6. Withdrawal of Patients

Patients will be informed that they have the right to withdraw from the study at any time for any reason, without prejudice to their medical care. The Investigator also has the right to withdraw patient from the study for any of the following reasons:

- Adverse event
- Concurrent medical condition
- Patient unwillingness to comply with study requirements
- Patient death
- Other Investigator decision

If a patient is withdrawn or discontinued from the study, the reason for withdrawal will be recording in the source documents and on the End of Study CRF. All patients withdrawn from the study will be encouraged to complete, if possible, all clinical evaluations scheduled for the 12 month follow-up visit. All adverse events will be followed as described in Section 7. Patients who are withdrawn from the study for any reason will not be replaced. The Principle Investigator may terminate the study at any time.

7. Adverse Events

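### Remote follow-up at months 1, 6 and 12 names no adverse event question, so 12-month AE incidence could be understated; separately, the AE window at month 24 is stated inconsistently

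*Combined protocol and SAP*

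**What the plan says.** **Remote contact in year 1.** The in-person list in Section 5.3 for months 1, 6 and 12 ends with "Review of concomitant medications and adverse events". Patients who are unable or unwilling to return are instead contacted by telephone, email or mail "to administer the IPSS and IIEF questionnaires, and to report any new treatments for BPH and/or LUTS". Section 9.3.3 defines the Safety Population as everyone who undergoes PAE, and Section 9.6.1 reports the number and percentage of patients with treatment-emergent AEs. The first secondary objective in Section 2.2 is "PAE-related adverse events", and the second is overall adverse events.

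**Month 24.** Section 4 states: "Following treatment, patients will return for follow-up visits at 1, 6, 12, and 24 months post PAE". It then lists what happens at every one of these visits, including "uroflowmetry and laboratory evaluations, and medication and adverse event reviews". It also says: "Treated participants will be followed for no less than 24 months". Section 7.1 has AEs assessed at every visit. Section 5.4, headed "Visit 5 (Long Term Follow-Up): 24 Months", lists neither an AE nor a medication review, and Appendix A leaves both rows blank at Visit 5. Sections 7.1, 7.2 and 7.3 use a 12-month period for recording and reporting. Sections 9.1 and 9.6 analyse at the 12-month lock. Section 6 encourages withdrawn patients to complete "all clinical evaluations scheduled for the 12 month follow-up visit".

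**The concern.** In a 20-patient, single-arm phase I/II study, AE incidence is one of the main results. Within the same 12-month window, men seen in person are asked about AEs, while men reached remotely are, on the written plan, asked about symptoms, sexual function and new treatment only. Both groups sit in one denominator. Active questioning is replaced by passive reporting for part of the cohort, and the summary tables would not show it.

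The month-24 conflict is a lesser matter. One section promises a review that the visit list and the schedule do not contain, so site staff cannot tell whether to ask about AEs at that visit or how to handle a clinically significant finding made there.

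**Working it through.** The plan states no expected AE rate, no sample size calculation and no expected number of remote patients, so there is no figure to reproduce. The check compares passages and adds simple arithmetic.

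**1. What each route collects at months 1, 6 and 12**
- In person (5.3; Appendix A, Visits 2 to 4): physical exam, vital signs, laboratory tests, ultrasound, uroflowmetry, both questionnaires, and AE and medication review.
- Remote (5.3): IPSS, IIEF and new BPH/LUTS treatments.
- Neither questionnaire (Appendices D and E) asks about hematuria, rectal bleeding or pelvic pain, which Section 5 names as prompts for cystoscopy or anoscopy. A remote patient also misses the exam, vital signs and laboratory tests that feed AE reporting under 9.6.2 to 9.6.4.

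**2. Direction of the error**
The denominator is all treated men (9.3.3). The missing-data rule in 9.5.7 covers efficacy variables only. An unrecorded event therefore counts as no event, and the error can only lower incidence.

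**3. Size per man**
With 20 treated (9.2), 1/20 = 5 percentage points. There are two conditions:
- 20 men are actually embolized. Section 4 counts enrolment from consent and Appendix C allows for no embolization, so the denominator could be smaller and one man worth more.
- The man has no other recorded event in the same summary row. If he already counts under any TEAE, a missed later event does not change that row.

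**4. Calendar time without a scheduled AE question, for a man remote at month 12**
A man missed at month 1 or 6 can be asked at a later visit. A man remote at month 12 has no later AE review under 5.4 and Appendix A. Taking the 12-month window as 52 weeks:
- Attended month 6 (week 24): 52 − 24 = 28 weeks; 28/52 = 54%. With the ±2-week visit window, 26 to 30 weeks, or 50% to 58%.
- Last attended month 1 (week 4): 52 − 4 = 48 weeks; 48/52 = 92%. With the visit window, 46 to 50 weeks, or 88% to 96%.

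This is calendar time, not a share of risk.

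**5. Illustration only**
Let n = 20, p = true 12-month incidence, m = men followed only remotely, and c = the chance that such a man's event is still captured. The values of p, m and c are assumptions.

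Expected observed incidence = p × (1 − (m/n) × (1 − c)). For p = 25%:

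| m | c = 0 | c = 0.5 | c = 1 |
|---|---|---|---|
| 2 | 22.5% | 23.75% | 25% |
| 4 | 20.0% | 22.5% | 25% |
| 6 | 17.5% | 21.25% | 25% |

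For example, with m = 4 and c = 0: 0.25 × (1 − 4/20) = 0.20.

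The chance of seeing at least one event with a true rate of 5% is 1 − (1 − p)^(n − m) × (1 − p × c)^m. With c = 0 it falls from 64.2% (m = 0) to 60.3%, 56.0% and 51.2% for m = 2, 4 and 6.

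**6. Month 24**
- Section 4 gives AE review at months 1, 6, 12 and 24, which is 4 visits. Section 5.3 and Appendix A give it at months 1, 6 and 12, which is 3. The last listed review falls at week 52 ± 2, that is, weeks 50 to 54.
- The blank in Appendix A is not proof alone, because the same column omits uroflowmetry, which 5.4 lists. The Appendix B chart is not readable in the text reviewed.
- Month 24 still includes physical exam, vital signs and laboratory tests (5.4). Sections 9.6.2 to 9.6.4 make clinically significant worsened findings AEs with no stated time limit, while 7.2 ends AE documentation at 12 months. A month-24 finding thus falls under two rules.

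**The case against.** **On remote contact.** The text says what the contact is for and does not exclude AE questions. Appendix A marks AEs at Visits 2 to 4 with no exemption for remote patients, 7.2 requires investigators to document every AE in the window, and 7.1 tells patients to report AEs themselves. IPSS, IIEF and the question on new treatments can reveal some urinary or sexual harms. All of this stands, and it is why incidence could be, rather than will be, understated. It does not close the gap: a duty to document reaches only events that become known, and none of these is a scheduled AE question in the remote contact.

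**On month 24.** Most passages agree on a 12-month window, 9.7 refers to 5.4 for the month-24 data, and the sentence in 7.1 about every visit is followed directly by one on the 12-month period. This also stands. The conflict is mainly the wording of Section 4.

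**Stronger readings.** A reader might infer that safety information is not collected at all after month 12. The documents do not support that. Month 24 has exam, vital signs and laboratory tests. Section 5 provides for cystoscopy or anoscopy for signs of injury throughout the study, 7.2 follows treatment-related AEs to resolution or a fatal outcome, and the bladder and rectal injury sentence in 7.3 has no time limit. A reader might also infer that the month-24 omission biases the planned incidence. It does not, because 9.6 analyses at the 12-month lock.

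**Conclusion.** The main point holds: as written, remote follow-up in year 1 names no AE question while the men concerned stay in the denominator, so 12-month AE incidence could be understated and cannot be overstated by this route. The total is unknown. The 5-point figure assumes 20 treated men and a missed event that is the man's only one in that row. The figures of 28 and 48 of 52 weeks depend on which visit he last attended. The bias is zero if nobody is followed remotely or if every event is captured another way.

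The month-24 point holds as a minor contradiction. What is missing is a scheduled AE and medication review, or a statement that none is intended, together with a clear rule for findings made at that visit. The planned 12-month incidence is not affected.

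**What to change.** **Main change.** Add a short AE/SAE question set to the telephone, email or mail contact in 5.3. Report how many men were asked about AEs at each time point, separately for in-person and remote contact.

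**Minor change.** Reconcile Section 4, 5.4, 7.1 to 7.3, 9.6.2 to 9.6.4 and Appendix A to one stated AE window, and check Appendix B against it. Either of two routes would do:
- Add AE and medication review to 5.4 and to Visit 5 in Appendix A, extend the remote question set to 5.4, keep 0 to 12 months as the planned safety summary, and give a separate 24-month summary.
- Correct Section 4 and the sentence in 7.1 about every visit, say how month-24 findings are handled, and state that AEs are not systematically reviewed after month 12.

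**Cost.** Protocol wording and a few CRF lines at contacts that already take place, with more events to record and no new procedure. The first route also adds a further year of SAE reporting under 7.3 and a safety summary beyond the 12-month lock.
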